6.1.1. Phase 1b Dose Escalation

This portion of the study is a single-arm, dose escalation study of PEGPH20 in combination with pembrolizumab subjects with relapsed/refractory NSCLC after failing at least 1 previous platinum-based therapy (refer to Inclusion Criterion #2) and subjects with relapsed/refractory gastric adenocarcinoma after failing at least 1 previous chemotherapy regimen. Using a standard 3+3 dose escalation design, approximately 3 to 6 subjects in each cohort will receive PEGPH20 + pembrolizumab. PEGPH20 will be administered on Day 1, Day 8 and Day 15 of each 21-day cycle to consecutive cohorts in increasing dose levels (1.6, 2.2, 2.6, 3.0, and 4.0 μ g/kg). Pembrolizumab will be administered on Day 1 of each cycle, 4-6 hours after the dose of PEGPH20. If the MTD is not reached at 4.0 μ g/kg, higher doses may be evaluated. If \geq 2 subjects experience a DLT at the 1.6 μ g/kg dose level, Cohort -1 will be opened and subjects will be dosed at 1.0 μ g/kg on Day 1, Day 8 and Day 15 of each 21-day cycle. The RP2D of PEGPH20 will be the MTD determined in Dose Escalation or the Sponsor may decide to choose a dose lower than the MTD and which has completed evaluation in Dose Escalation and is found to be safe and tolerable to evaluate in Dose Expansion.

The number of cohorts studied and number of subjects exposed to a given dose level will depend on the doses tested. It is anticipated that up to 5 dose levels will be studied for a total of approximately 30 subjects exposed to study medication. The dose allocation for 5 cohorts of subjects assigned to the 5 preselected dose levels and 1 cohort assigned to the preselected dose of $1.0 \,\mu\text{g/kg}$ (if ≥ 2 subjects experience a DLT at $1.6 \,\mu\text{g/kg}$ dose level) is shown as an example in Table 4. The study medication dosing and treatment schedule are shown in Table 5.

Safety data from all subjects dosed will be reviewed to determine the RP2D. Dose escalation will be guided by safety data from each subject during the 21 days following their first dose of PEGPH20. Intra-subject dose escalation to the next PEGPH20 dose studied may be allowed if the Investigator deems it in the best interest of the subject and after discussion with the Sponsor and provided the next PEGPH20 dose studied has been determined not to have exceeded the MTD.

- If none of 3 subjects in a given cohort experience a DLT within 21 days of starting treatment, enrollment and dosing may proceed at the next planned dose level.
- If 1 of 3 subjects at a given dose level experiences a DLT within the first 21 days of treatment, 3 additional subjects will be enrolled and dosed at the dose level at which the DLT occurred. If ≤1 of 6 subjects experience a DLT, dose escalation will continue to the next planned higher dose.
- If ≥2 subjects at a given dose level experience a DLT within the first 21 days of treatment, that dose level will be considered to have exceeded the MTD and dose escalation will be stopped. If the previous dose level did not already have 6 subjects treated with ≤1 DLT, enrollment and dosing will then resume in the previous dose level with additional subjects up to a total of 6 subjects. The highest dose level at which no more than 1 of 6 evaluable subjects has experienced a DLT in the first 3 weeks of treatment will be considered the MTD for the PEGPEM combination. The RP2D will be based on the overall safety profile.

• If \geq 2 subjects at the 1.6 µg/kg dose level experience a DLT within the first 21 days of treatment, Cohort -1 will be opened at a lower dose level of 1.0 µg/kg.

Note: Additional subjects may be enrolled in each cohort to further assess the tolerability of PEGPEM and determine an acceptable safety profile prior to the enrollment in the next dose level and expansion portion of the study.

Definition of DLT

DLTs will be assessed for each subject during the 21 days following their first PEGPH20 dose and will be defined as any of the following:

- Any treatment-emergent Grade ≥3 toxicity that is considered related to either PEGPH20 or pembrolizumab or the combination of PEGPH20 and pembrolizumab (nausea, vomiting, musculoskeletal events and diarrhea will be considered DLTs only if they reach ≥ Grade 3 despite adequate supportive care measures).
- Grade 3 MSEs are considered DLTs only if they do not reduce to ≤ Grade 2 within 48 hours despite therapeutic intervention.
- Hypersensitivity/infusion reactions related to PEGPH20 or pembrolizumab dosing will not be considered DLTs (hypersensitivity reactions are generally not related to the dose level of a drug since they can occur even upon a low level of exposure).

To be considered evaluable for DLT assessment, subjects must receive 1 of the 3 full planned doses of PEGPH20 and 1 complete dose of pembrolizumab in Cycle 1. Subjects who experience a DLT within the first 21 days of treatment and withdraw from the study will be considered evaluable for DLT and will not be replaced. Subjects who withdraw within the first 21 days for reasons other than a DLT will be considered not evaluable and will be replaced. Any PEGPH20 treatment-related AE that results in interruption or reduction of either drug (PEGPH20 or pembrolizumab) may be considered a DLT at the Investigator's discretion.

The Sponsor and the participating Investigators will meet as soon as practical, post completion of a cohort, and no more than 10 business days after the end of the last cohort to determine an acceptable dose for the Dose Expansion portion after reviewing all available safety data from Cycle 1 from all subjects in the Dose Escalation portion.

Table 4: Dose Allocation and Cohort Schedule - Dose Escalation Portion

Dose Level	PEGPH20 μg/kg	Pembrolizumab mg/kg
-1	1.0	2
1	1.6	2
2	2.2	2
3	2.6	2
4	3.0	2
5	4.0^{a}	2

Abbreviations: PEGPH20 = PEGylated Recombinant Human Hyaluronidase.

Note: Each treatment cycle is 21 days. Dose interruption and modifications are permitted.

^a If the MTD is not reached at 4.0 μg/kg, higher doses may be evaluated.

6.1.2. Phase 1b Dose Expansion

Approximately 51 HA-high subjects will be studied in the Dose Expansion portion at the RP2D identified in the Dose Escalation portion:

- Approximately 30 subjects with Stage IIIB or IV NSCLC, previously untreated or treated and having failed no more than 1 previous platinum-based chemotherapy (refer to Inclusion Criterion #3)
- Approximately 21 subjects with relapsed/refractory gastric adenocarcinoma having failed no more than 2 previous chemotherapy regimens.

The study medication dosing and treatment schedule are shown in Table 5.

Table 5: Study Medication Dosing and Treatment Schedule - Dose Escalation and Dose Expansion

Time point	PEGPEM Treatment	
Subjects with NSCLC or Gastric Adenocarcinoma		
Cycle 1 and Beyond (Each Cycle 21 Days)		
Week 1		
Day 1	PEGPH20	
	Pembrolizumab (4-6 hours after PEGPH20)	
Week 2		
Day 8	PEGPH20	
Week 3		
Day 15	PEGPH20	

Abbreviations: PEGPEM = PEGPH20 in combination with pembrolizumab; PEGPH20 = PEGylated Recombinant Human Hyaluronidase; NSCLC = non-small cell lung cancer.

Notes: Dose interruption and modifications are permitted; refer to Section 8.3 for further guidance. Visit window is ± 2 days of the specified times.

6.1.3. Study Duration

The study will consist of a Screening period of up to 28 days, a treatment period (21-day cycles), a 30-day post-treatment period (after last dose) for collection of AEs and a long-term follow-up. Subjects will be allowed to continue treatment on study until disease progression (as defined in Section 6.1.4) or unacceptable toxicity. Subjects with asymptomatic disease progression however, will be allowed to continue the study treatment at the Investigator's discretion despite evidence of increasing tumor burden or appearance of new lesions for up to 6 weeks if the subject is clinically stable.

Investigators may also discontinue study treatment if it is no longer in the best interest of the subject. Subjects who discontinue treatment with PEGPH20 and pembrolizumab will be followed every 12 weeks for survival until death, withdrawal of consent, or lost to follow-up.

6.1.4. Disease Progression

Disease progression will be defined as presence of 1 or both of the following:

Disease progression documented by CT scan/MRI scan based on RECIST v1.1 (Eisenhauer 2009; Appendix C) as determined by the Investigator.

Clinical tumor-related progression that is well documented in the absence of scans demonstrating radiographic disease progression.

Radiographic disease progression is based on the analysis of CT/MRI scans by the Investigator. Investigators should continue study treatment until disease progression (not including asymptomatic disease progression in clinically stable subjects [see Section 6.1 for definition of clinically stable]) has occurred, but may discontinue study treatment if there is documented clinical disease progression and/or unacceptable toxicity and/or study treatment is no longer in the best interest of the subject. Subjects who discontinue treatment with PEGPH20 and pembrolizumab will be followed every 12 weeks for survival until death, withdrawal of consent, or lost to follow-up.

7. SELECTION AND WITHDRAWAL OF SUBJECTS AND STUDY TERMINATION

The Dose Escalation portion of the study will enroll subjects with relapsed/refractory Stage IIIB or IV NSCLC after failing at least 1 previous platinum-based chemotherapy regimen (refer to Inclusion Criterion #2) and subjects with relapsed/refractory locally advanced or metastatic gastric adenocarcinoma after failing at least 1 previous chemotherapy regimen for locally advanced or metastatic disease.

The Dose Expansion portion of the study will enroll:

• HA-high subjects with Stage IIIB or IV NSCLC, previously untreated or treated and having failed no more than 1 previous platinum-based chemotherapy (refer to Inclusion Criterion #3), who have tissue available for HA-selection and PD-L1 testing

and

 HA-high subjects with relapsed/refractory locally advanced or metastatic gastric adenocarcinoma having failed no more than 2 previous chemotherapy regimens for locally advanced or metastatic disease, who have tissue available for HA-selection and PD-L1 testing.

7.1. Inclusion Criteria

For both portions of the study (unless otherwise specified), subjects must satisfy all of the following inclusion criteria to be enrolled in the study:

- 1. Written Institutional Review Board (IRB)/Ethics Committee (EC) -approved Informed Consent form (ICF), signed by subject or legally authorized representative.
- 2. Dose Escalation portion Histologically confirmed and documented, previously treated stage IIIB or IV NSCLC having failed at least 1 previous platinum-based chemotherapy regimen for locally advanced or metastatic disease, or relapsed/refractory locally

advanced or metastatic gastric adenocarcinoma having failed at least 1 previous chemotherapy regimen for locally advanced or metastatic disease. Subjects with NSCLC who are known to be epidermal growth factor receptor (EGFR)-mutation positive must have received an EGFR inhibitor and subjects known to be anaplastic lymphoma kinase (ALK)-mutation positive must have received an ALK inhibitor (subject's documented EGFR/ALK mutation status and/or confirmation reports/molecular pathology/analysis reports should be included in the subject's medical records and made available for Sponsor/Sponsor representative[s] review).

- a. Subjects with gastroesophageal junction (GEJ) tumors are eligible.
- b. For subjects with either NSCLC or gastric cancer, prior treatment administered in the adjuvant setting is permitted provided it was administered at least 6 months prior to first-line therapy for metastatic disease.
- c. For subjects with NSCLC, prior first-line treatment with bevacizumab (AVASTIN®) or biosimilars is allowed.
- d. For subjects with NSCLC, prior maintenance treatment with bevacizumab, pemetrexed (ALIMTA®), or erlotinib (TARCEVA®) is allowed.
- e. For subjects with human epidermal growth factor receptor 2 positive (HER2+) gastric cancer, prior treatment with trastuzumab (HERCEPTIN®) is required (subject's documented HER2 status and/or confirmation reports/molecular pathology/analysis reports should be included in the subject's medical records and made available for Sponsor/Sponsor representative[s] review).
- 3. Dose Expansion portion NSCLC subjects: Histologically confirmed and documented, previously untreated or treated stage IIIB or IV NSCLC. Previously treated subjects must have failed no more than 1 previous platinum-based chemotherapy regimen for locally advanced or metastatic disease. Previously treated subjects with NSCLC who are known to be EGFR-mutation positive must have received an EGFR inhibitor and subjects who are known to be ALK-mutation positive must have received an ALK inhibitor (subject's documented EGFR/ALK mutation status and/or confirmation reports/molecular pathology/analysis reports should be included in the subject's medical records and made available for Sponsor/Sponsor representative[s] review). Gastric adenocarcinoma subjects: histologically confirmed and documented previously treated relapsed/refractory locally advanced or metastatic gastric adenocarcinoma having failed no more than 2 previous chemotherapy regimens for locally advanced or metastatic disease.
 - a. Subjects with GEJ tumors are eligible.
 - b. For subjects with either NSCLC or gastric cancer, prior treatment administered in the adjuvant setting is permitted provided it was administered at least 6 months prior to first-line therapy for metastatic disease.
 - c. For previously treated subjects with NSCLC, prior treatment with or without bevacizumab (AVASTIN®) or bevacizumab biosimilars is allowed.
 - d. For previously treated subjects with NSCLC, prior maintenance treatment with bevacizumab, pemetrexed (ALIMTA®), or erlotinib (TARCEVA®) is allowed.
 - e. For subjects with HER2+ gastric cancer, prior treatment with trastuzumab (HERCEPTIN®) is required (subject's documented HER2 status and/or confirmation reports/molecular pathology/analysis reports should be included in the subject's medical records and made available for Sponsor/Sponsor representative[s] review).

- 4. Prior to enrollment, confirmation of the following must be obtained:
 - a. **Dose Escalation portion** Available tumor tissue in a formalin-fixed paraffin-embedded (FFPE) block or 5-10 unstained consecutive core biopsy slides from 1 tumor tissue block that meet specific tissue sample requirements are preferred but not mandatory for enrollment in this portion of the study. **Note:** Fine needle aspirates or brushing biopsies will not be acceptable.
 - b. **Dose Expansion portion -** Available tumor tissue in FFPE block or 10-15 unstained consecutive tumor tissue slides from 1 tumor tissue block that meet specific tissue sample requirements are mandatory. **Note:** Fine needle aspirates or brushing biopsies will not be acceptable. Archived resection specimens from the primary tumor without radiologic evidence of metastasis at the time of resection are not suitable to establish histological confirmation and require new tumor tissue of a metastatic site.
- 5. To be eligible for the Dose Escalation portion, subjects need only have evaluable disease (details in Section 8.2.15); to be eligible for the Dose Expansion portion, subjects must have measurable disease per RECIST v1.1. Previously irradiated tumors may be eligible if they have clearly progressed in size.
- 6. Eastern Cooperative Oncology Group (ECOG) Performance Status of 0 or 1 (Appendix B).
- 7. Life expectancy ≥ 3 months.
- 8. Males and females aged \geq 18 years.
- 9. Resolution of all acute toxic effects of prior therapy or surgery to baseline.
- 10. Screening clinical laboratory values are as follows:
 - a. Total and indirect bilirubin $\leq 1.5 \times$ upper limit of normal (ULN), except for Gilbert's syndrome
 - b. Aspartate aminotransferase (AST), alanine aminotransferase (ALT), and alkaline phosphatase (ALP) $\leq 2.5 \times \text{ULN}$ ($\leq 5 \times \text{ULN}$ is allowed if liver metastases are present)
 - c. Serum creatinine ≤1.5 mg/dL or calculated creatinine clearance ≥40 mL/min
 - d. Serum albumin >3.0 g/dL
 - e. Hemoglobin ≥10 g/dL (transfusion and erythropoietic agents allowed)
 - f. Absolute neutrophil count ≥1500 cells/mm³
 - g. Platelet count $\geq 100,000/\text{mm}^3$
- 11. Female participants of childbearing potential (WOCBP) must have a negative urine or serum pregnancy test within 7 days before Day 1 (first dose of study medication).
- 12. For WOCBP and for men, agreement to use an effective contraceptive method from the time of screening throughout the study until 4 months (WOCBP) or 3 months (men) after administration of the last dose of any study medication. Highly effective contraceptive methods consist of prior sterilization, intrauterine device (IUD), intrauterine hormone releasing system (IUS), oral or injectable contraceptives, and/or barrier methods. Abstinence alone is not considered an adequate contraceptive measure for the purposes of this study.

- 13. Subjects must also satisfy the following inclusion criterion to be enrolled in the Dose Expansion portion of the study:
 - a. Subjects (NSCLC and gastric adenocarcinoma) must be determined to have HA-high levels from their tumor biopsies. Tumor samples must meet the requirements noted in the Inclusion Criterion #4.
 - b. NSCLC and gastric adenocarcinoma subjects must have tissue available for HA-selection and PD-L1 testing. Tumor samples must meet the requirements noted in the Inclusion Criterion #4.

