7.2. Exclusion Criteria

Subjects are ineligible for enrollment if they meet any of the following exclusion criteria.

- 1. Previous treatment with pembrolizumab, nivolumab, or other anti-PD-1 or anti-PD-L1 agents.
- 2. New York Heart Association Class III or IV (Appendix D) cardiac disease or myocardial infarction within the past 12 months before screening, or preexisting atrial fibrillation.
- 3. History of cerebrovascular accident or transient ischemic attack.
- 4. NSCLC subjects with known brain metastases (exception below)
 - a. Subjects with treated brain metastases who meet all of the following criteria are eligible:
 - i. Stable brain metastases for at least 1 month,
 - ii. No evidence of progression or hemorrhage after treatment,
 - iii. No ongoing requirement for corticosteroids.
- 5. Gastric adenocarcinoma subjects with brain metastases.
- 6. History of active bleeding within the last 3 months requiring transfusion.
- 7. Anti-angiogenic therapy within the last month.
- 8. Subjects with known interstitial fibrosis or interstitial lung disease.
- 9. History of pulmonary embolism or pulmonary embolism found on screening exam.
- 10. Pre-existing carotid artery disease.
- 11. History of DVT with contraindications to pharmacologic anticoagulation.
- 12. History of:
 - a. Pneumonitis that requires oral or IV steroids;
 - b. Or known cases of hepatobiliary diseases (e.g., primary biliary cholangitis, primary sclerosing cholangitis, history of immune-mediated cholangitis);
 - i. Subjects with cholangitis attributed to infectious etiology (e.g., ascending cholangitis, bacterial cholangitis) are eligible if the infection has been fully resolved prior to the screening visit.
 - c. Or known cases of drug-induced hepatobiliary toxicities.

- 13. NSCLC subjects with hypersensitivity to aspirin.
- 14. Gastric adenocarcinoma subjects with contraindications to enoxaparin.
- 15. Autoimmune diseases:
 - a. Active autoimmune disease requiring systemic treatment within the past 3 months
 - b. Documented history of clinically severe autoimmune disease (e.g., colitis, Crohn's disease)*
- 16. Active, uncontrolled bacterial, viral, or fungal infection requiring systemic therapy.
- 17. Known infection with human immunodeficiency virus, active infection with hepatitis B, or hepatitis C.
- 18. Known allergy to hyaluronidase.
- 19. Hypersensitivity to the active substance or ingredients of PEGPH20 and pembrolizumab.
- 20. Known allergy to piroxicam or other NSAIDs.

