9.1.2. Pembrolizumab

Pembrolizumab is a human programmed death receptor-1-blocking antibody indicated for the treatment of patients with unresectable or metastatic melanoma; patients with metastatic NSCLC whose tumors express PD-L1 as determined by an FDA-approved test and who have disease progression on or after platinum-based chemotherapy (patients with EGFR or ALK genomic tumor aberrations should have disease progression on FDA-approved therapy for these aberrations prior to receiving pembrolizumab); and patients with recurrent or metastatic head and neck squamous cell carcinomas with disease progression on or after platinum-based chemotherapy.

Pembrolizumab will be considered investigational for the purpose of this study since the combination of pembrolizumab with PEGPH20 has not been indicated as yet for the treatment of the populations studied in this trial.

Refer to the Keytruda Prescribing Information for a thorough description and diagram of the structure of pembrolizumab (Keytruda® US Prescribing Information 2017).

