11.1.2. Sample Size

In the dose escalating portion, there may be up to 5 dose levels for a total of approximately 30 subjects.

In the Dose Expansion portion, approximately 51 subjects with HA-high tumors will be enrolled (30 with HA-high tumors in NSCLC cohort and 21 with HA-high tumors in the gastric adenocarcinoma cohort).

KEYNOTE-001 study data presented at the American Society of Clinical Oncology 2016 (Hui 2016) showed that when treated with pembrolizumab alone, treatment naïve subjects who had evaluable PD-L1 Tumor Proportion Score [TPS] levels had an ORR of 29% and previously treated subjects who had evaluable PD-L1 TPS levels had an ORR of 21%. Under the assumption that no more than 40% of the subjects enrolled in this study will be treatment naïve, ORR in the combined NSCLC population is expected to be approximately 24% when treated with pembrolizumab alone. A 20% improvement in ORR is considered clinically meaningful when PEGPH20 is added to pembrolizumab. Under these conditions, 30 NSCLC subjects would provide approximately 80% power at the hypothesized ORR of 44% when the null hypothesis H0: ORR ≤24% is tested against H1: ORR >24% using an exact one-sided binomial test at a 10% significance level.

KEYNOTE-012 study data showed that the ORR in PD-L1 positive gastric cancer subjects is about 22% (Muro 2016). Since subjects will not be selected based on PD-L1 expression levels prospectively in this study, in order to accommodate all subjects (irrespective of PD-L1 expression levels), a conservative ORR of 15% is assumed with pembrolizumab treatment alone and it is further assumed that the addition of PEGPH20 to pembrolizumab will lead to a clinically meaningful improvement of 20% in ORR to 35%. Under these assumptions, 21 subjects will provide approximately 80% power at the hypothesized ORR of 35% when the null hypothesis H0: ORR ≤15% tested against H1: ORR >15% using an exact one sided binomial test at a 10% significance level.

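### Dose Expansion lets a subject with untreated NSCLC and a known EGFR mutation receive first-line PEGPEM before any targeted therapy

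*Protocol*

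**What the plan says.** **Dose Expansion, criterion 3** (Protocol Section 7.1, same wording in the Synopsis). NSCLC subjects may be untreated or treated. For the treated, "Previously treated subjects must have failed no more than 1 previous platinum-based chemotherapy regimen for locally advanced or metastatic disease". The mutation rule follows: "Previously treated subjects with NSCLC who are known to be EGFR-mutation positive must have received an EGFR inhibitor". The ALK clause in the same sentence does not repeat the treated-subject qualifier. Sub-item c, on bevacizumab, carries the qualifier too: "For previously treated subjects with NSCLC, prior treatment with or without bevacizumab". Sub-item d, on maintenance therapy, does the same.

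**Dose Escalation, criterion 2** (Section 7.1). The rule has no qualifier: "Subjects with NSCLC who are known to be epidermal growth factor receptor (EGFR)-mutation positive must have received an EGFR inhibitor". Every NSCLC subject in that portion has already failed platinum chemotherapy.

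**Exclusions** (Section 7.2). "Subjects are ineligible for enrollment if they meet any of the following exclusion criteria". The list of 26 mentions neither EGFR nor ALK. Number 25 is a general clause covering conditions that contraindicate an investigational drug, may affect interpretation, or raise the risk of complications.

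**Documentation.** Criterion 3 asks that EGFR/ALK status be kept in the medical record and be open to Sponsor review. Section 8.2.17.1.1 asks for any molecular pathology reports. Neither requires an EGFR or ALK test.

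**Drug description** (Section 9.1.2). Within the indication for PD-L1-expressing NSCLC after platinum, the text covers patients "who have disease progression on or after platinum-based chemotherapy (patients with EGFR or ALK genomic tumor aberrations should have disease progression on FDA-approved therapy".

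**The concern.** Two features of criterion 3 combine badly. It opens the cohort to first-line NSCLC, and it confines the EGFR-inhibitor rule to subjects already treated. A subject in the first group with a known EGFR mutation meets no bar. Once enrolled, that subject cannot be given an EGFR inhibitor alongside study treatment, because Section 8.4 prohibits other anti-cancer agents on study. Targeted therapy would wait until PEGPEM is stopped.

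What is at stake is the subject's treatment sequence. The protocol requires an EGFR inhibitor beforehand of every other known EGFR-positive NSCLC subject, in both portions of the study.

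**Working it through.** No figure in the plan rests on this clause, so the check is mainly one of reading.

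**Step 1. Who is covered by the EGFR rule?**

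| Known EGFR-positive NSCLC subject | Criterion | Inhibitor required first? |
|---|---|---|
| Dose Escalation (all pretreated) | 2 | Yes |
| Dose Expansion, previously treated | 3 | Yes |
| Dose Expansion, previously untreated | 3 | No |

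For ALK, the third row is unclear: the clause can stand alone or share the qualifier.

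**Step 2. Does anything else bar the third row?** The exclusion list in the Synopsis and in Section 7.2 has no EGFR or ALK item. Exclusion 25 depends on judgement and does not mention mutation status. Record-keeping and report submission mean that the site and Sponsor may know of the mutation, but enrolment would still comply with the protocol.

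**Step 3. Is the eligibility explained?** Section 4.6 and its subsections do not discuss EGFR or ALK. Nor do the SAP sections on design (3.1) and sample size (4.12).

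**Step 4. Can the effect on ORR be sized?** It would need the number of untreated subjects, the share with a known mutation, and their response rate.

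- *Untreated subjects.* Section 11.1.2 reads "Under the assumption that no more than 40% of the subjects enrolled in this study" would be treatment naïve. On the planned 30 that is 0.40 × 30 = 12. It reproduces the design rate: 0.40 × 29% + 0.60 × 21% = 24.2%, against the stated 24%. But it is a planning assumption. Neither criterion 3 nor Section 6.1.2 caps untreated enrolment, so it sets no upper limit for the 30 planned or the 17 enrolled.
- *Share with a known mutation.* No EGFR prevalence is given. Since testing is not mandated, the known share could be below any overall prevalence.
- *Adjusting for histology.* Suppose the mutations occur only in adenocarcinoma (an assumption). Section 4.1 gives histology shares of 50/30/10% (adenocarcinoma, squamous, large cell), which total 90%. Section 4.6.3 gives HA-high rates of 11/41/33%. The HA-high total is 0.50 × 0.11 + 0.30 × 0.41 + 0.10 × 0.33 = 0.055 + 0.123 + 0.033 = 0.211. If the unlisted 10% are never HA-high, the adenocarcinoma share becomes 0.055/0.211 = 26.1%, a factor of 26.1/50 = 0.52. If they follow the average of the rest, the factor is 0.11/(0.211/0.90) = 0.47. Neither 21.1% nor 0.211/0.90 = 23.4% matches the 29% HA-high that Section 4.6.3 reports, so the two sections describe different tissue mixes.
- *Response rate.* None is given for EGFR-positive subjects. The documents also do not say whether the 29% untreated benchmark population included them, so the comparison with the null rate might already be partly like with like.

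The first input is an uncapped assumption, and the other two are missing. Any ORR shift would restate the values chosen for them.

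**The case against.** The strongest reply is that the qualifier follows from the design. An untreated subject cannot have had an EGFR inhibitor, so a rule requiring one can apply only to treated subjects. Sub-items c and d were worded the same way, and the Synopsis agrees with Section 7.1, so the drafting looks deliberate. Criterion 2 needs no qualifier because everyone it covers is pretreated. All of that stands, and it rules out calling criteria 2 and 3 contradictory. It does not close the gap, because the protocol could have made known-positive untreated subjects ineligible and did not.

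A second reply points to exclusion 25, Sponsor review, molecular reports and informed consent. These are real safeguards, but they depend on someone choosing to act, whereas for treated subjects the protocol states a rule.

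A third is that no passage says an untreated EGFR-positive subject must have targeted therapy first. A reader might infer from Section 9.1.2 that the protocol breaches the pembrolizumab label. It does not show that: the sentence sits inside the post-platinum, PD-L1-expressing indication. It is context that fits the approach taken elsewhere in the protocol. Nor would the absence of a rationale be a finding on its own, since most eligibility lines are not individually justified.

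**Conclusion.** The gap is real and minor. As written, criterion 3 allows a known EGFR-positive subject with untreated NSCLC to receive investigational PEGPEM first line, and nothing else in the eligibility rules prevents it. The EGFR reading is unambiguous; for ALK the text is only unclear.

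Two stronger readings are tempting and unsupported. One is that the primary ORR was distorted by a calculable amount: the inputs are missing, and even the direction relative to the null rate depends on what the benchmark population contained. The other is that such subjects were treated. SAP Section 4.7.2 reports 17 NSCLC subjects enrolled in Dose Expansion, and neither document gives their mutation status.

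**What to change.** In criterion 3, in both the Synopsis and Section 7.1:

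- Keep the inhibitor requirement for previously treated subjects and word it so that it plainly covers both EGFR and ALK.
- Add: *Previously untreated subjects with NSCLC known to be EGFR- or ALK-mutation positive are not eligible.*

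Keeping the phrase *known to be* means that no new testing is imposed.

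**Cost.** One sentence revised and one added, in two places. A few candidates become ineligible until they have received the inhibitor. They could then enter as previously treated without any platinum, because a limit of no more than one regimen allows none. That route already exists under the present text, so the change does not create it. How such subjects compare with the 21% benchmark for previously treated disease is unknown.

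Because enrolment ended on 31 May 2018 (SAP Section 4.7.2), the amendment matters only for reopening the study or reusing its wording. For this trial, an optional step is to list EGFR/ALK status for the 17 NSCLC subjects. The baseline summaries in SAP Section 4.6.2 do not include it. The data may have to be abstracted from medical records, since the protocol does not say they are in the eCRF.
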